Oral mucositis in advanced stages, similar to a FGG donor site, can be extremely painful, preventing a patient from eating and even disrupting the patient's daily functions. The aim of this study will be to compare patient-based outcomes, specifically postoperative pain, at the FGG donor sites, using an interventional parallel-group design, whereby a hemostatic gauze, Surgicel®, will be placed within all of the palatal donor sites and covered with either episil® (test) or a cyanoacrylate dressing, PeriAcryl®90 (control). The secondary aim of this study will be to compare gingival healing via measurement of the gingival blood flow at the FGG donor sites by the laser Doppler flowmetry (LDF) technique, by monitoring blood perfusion. The hypothesis for the present study is that patient-based outcomes and gingival blood flow will be more favorable for the FGG donor sites being covered by the test wound dressing material episil® compared to the control dressing.

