#### *Study Population and Design*

Forty subjects will be recruited from the Periodontics and Dental Hygiene Clinic and the UTDentists Practice, located at the UTHealth School of Dentistry in Houston, Texas, where the study will be performed. Only subjects who have already formally agreed to receive a FGG as part of their overall periodontal treatment plan will be recruited. Inclusion criteria will be 18 years of age or older, patient of record at UTHealth School of Dentistry Houston Texas, signed treatment plan for a FGG, and the ability to provide research informed consent. Exclusion criteria will be any allergies to any of the ingredients in episil® including allergies to peanuts, soy or peppermint oil, smokers, pregnant or breast feeding women, and inability or unwillingness to provide informed consent. As stated above, elective surgical procedures are not routinely performed on pregnant or lactating women and are postponed until after childbirth and or completion of lactation. Exit criteria will be unwillingness or inability to continue in the study and non-compliance with study procedures and appointments. The Institutional Review Board of The University of Texas will approve the study protocol, questionnaires and informed consent form.

The study will be of an interventional parallel-group design. A computer generated randomization scheme will assign the subjects to one of the two treatment groups. All subjects will have the gingival grafting procedure, the free gingival graft, performed at sites lacking attached keratinized gingival tissues. The palatal donor site in subjects assigned to the control group will receive the hemostatic agent, Surgicel®, covered by the cyanoacrylate dressing, PeriAcryl®90. The palatal donor site in the subjects assigned to the test group will receive the hemostatic agent, Surgicel®, covered by episil®. Additionally, the subjects in the test group will be given the remainder of the bottle of episil® to take home with

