One of the secondary outcomes, gingival blood flow, will be determined with the laser Doppler flowmetry (LDF) technique to measure the blood perfusion of the FGG donor site and as well as the contralateral side of the palate, as a positive control, at baseline prior to surgery, immediately after harvesting of the FGG from donor site, and on post-operative days 3, 7, 14 and 21. The LDF technique is an unbiased non-invasive method of monitoring the response to periodontal therapy. It is adequate for recording changes in gingival blood flow following periodontal surgery presenting different patterns of microvascular blood flow alterations during the wound-healing period. The LDF technique is based on the Doppler principle. A laser beam will be emitted by an optical fibre onto the FGG donor site. The light hitting moving erythrocytes is scattered back in shifting frequency, which is the Doppler effect, and is captured by one or more optical fibers. The light signals are then converted into electric signals and the resulting photocurrent is processed to provide a recording of the blood flow. The term used to describe blood flow is flux – a quantity proportional to the average speed of the blood cells and their concentration. This is expressed in arbitrary perfusion units (PU), which are linearly related to flux. The PeriFlux System 5000 (Laser Doppler Blood Perfusion Monitoring and  $\text{tcpO}_2/\text{tcpCO}_2$ ) along with the Laser Doppler Probes for the PeriFlux System 5000 will be used to perform the LDF technique.

The other secondary outcome will be the time needed to obtain a complete re-epithelialization of the FGG donor site, and will be performed by a non-invasive peroxide test. This test is based on the principle that if the epithelium is discontinuous, the  $\text{H}_2\text{O}_2$  diffuses into the connective tissue; the enzyme catalase acts on  $\text{H}_2\text{O}_2$  to release water and oxygen: this is clinically shown by the production of bubbles on the wound. 3%  $\text{H}_2\text{O}_2$  will be applied to the FGG donor site with a syringe and the appearance of bubbles will be recorded as a dichotomous variable (yes/no) at the post-operative days 3, 7, 14, and 21 until a subject's FGG donor site has

completely epithelialized (no bubbles observed), when they will not be measured again at future post-operative visits.

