**First clinic visit (Screening visit):** Discussion of study and attain informed consult for participation in the study; medical history will be updated, vital signs will be taken, and an upper arch alginate impression will be taken in order to create a plastic stent, which will be worn during the laser Doppler flow measurements.

**Second clinic visit (Day of Surgery):** The day of surgery, the laser Doppler flowmetry readings will be performed before the surgery and then again immediately after harvesting of the FGG donor site. Subjects will receive 4 copies of the Visual Analog Scale Form/Questionnaire to be completed at their homes on days 1, 2, 5, and 10 postoperatively, which will be labeled accordingly. Subjects assigned to the test group will receive a manual-metering pump containing sufficient episil® for the duration of the study. Subjects in the test group will be instructed to use the pump up to 3 times a day. Instructions for home application of the episil® will be given orally and in writing at this appointment.

**Day 1 post-operative:** All subjects will complete at home the Day 1 Post-Operative Visual Analog Scale Form/Questionnaire.

**Day 2 post-operative:** All subjects will complete at home the Day 2 Post-Operative Visual Analog Scale Form/Questionnaire.

**Day 3 post-operative (3rd clinic visit):** All subjects will bring the 2 completed Visual Analog Scale Forms/Questionnaires to the day 3 post-operative clinic appointment and will complete the Day 3 Post-Operative Visual Analog Scale Form/Questionnaire during this appointment. The laser Doppler flowmetry readings will be performed on the free gingival graft donor site and on the contralateral side of the palate utilizing the fabricated stent with holes for the Doppler probe positioning for repeatability of readings. 3% H2O2 will be applied to the FGG donor site with a syringe and the appearance of bubbles will be recorded as a dichotomous variable.

**Day 5 post-operative:** All subjects will complete at home the Day 5 Post-Operative Visual Analog Scale Form/Questionnaire.

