#### *Statistical Analysis*

Descriptive statistics will be expressed as means+/- SD and frequency distributions. Intergroup (FFG donor site using episil® and Surgicel® (test) and FGG donor site with PeriAcryl®90 and Surgicel® (control)) comparisons at 1, 2, 3, 5, 7, 10, 14 and 21 days will be analyzed by the Mann-Whitney U test. The Wilcoxon signed-rank test will be used for intragroup comparisons between 1, 2, 3, 5, 7, 10, 14 and 21 days. Differences in frequency distributions between the episil® group and the PeriAcryl®90 group will be analyzed by the Fisher exact test. Associations

between pain VAS scores and the number of analgesic pills or number of days analgesics were taken will be examined by the Pearson correlation coefficient. The significance level for rejection of the null hypothesis will be set at  $\alpha = 0.05$ .

All LDF recordings, which may be impaired by artifacts caused by the relative motion of the probe, will be excluded. An average of the 2-minute period of each individual recording will be calculated. Changes of blood flux values in the FGG donor site will be expressed as the difference ( $\Delta PU$ ) between the PU value at a specific site at a specific observation time point ( $PU_t$ ) and the individual baseline value of the same site ( $PU_0$ ):  $\Delta PU_t - PU_0$ .

Descriptive statistics will be performed using the SPSS statistical software. The  $\Delta PU$  values in the FGG donor site will be analyzed using the general linear model (GLM) univariate test, after verification of the assumptions of homogeneity of variance and normality of the residual distribution. The observation time and point and the position (mesial, center, distal and apical to the FGG donor site) will be modeled as fixed factors and the patient as a random factor with the  $\Delta PU$  as the dependent variable. The Dunnett two-sided *t*-test will be used, in order to evaluate the differences between baseline and subsequent time points and between different positions in the FGG donor site during the overall observational period. Data will be presented as mean SE. Statistical significance will be accepted at  $p < 0.05$ .

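### No masking is specified for whoever reads the peroxide test or rejects LDF recordings, so systematic unmasked judgement could bias both secondary comparisons

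*Combined protocol and SAP*

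**What the plan says.** **Peroxide test.** Under Study Population and Design, "the appearance of bubbles will be recorded as a dichotomous variable (yes/no) at the post-operative days 3, 7, 14, and 21". The reader is not named. Once no bubbles are seen the site counts as closed, "when they will not be measured again at future post-operative visits". The visit-by-visit timeline in Surgical Procedures & Postoperative Care lists the test at days 3, 7, 14 and 21 without that condition.

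**LDF.** Each recording is averaged over 2 minutes. Before that, the Statistical Analysis section states: "All LDF recordings, which may be impaired by artifacts caused by the relative motion of the probe, will be excluded". It gives no numerical criterion, names nobody to apply it and does not provide for reporting exclusions. Study Population and Design adds that "The LDF technique is an unbiased non-invasive method of monitoring the response to periodontal therapy".

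**Allocation and arms.** "A computer generated randomization scheme will assign the subjects to one of the two treatment groups"; nothing follows about masking of subjects, operators, readers or analysts. Control sites are covered with a cyanoacrylate and test sites with a gel. In addition, "Subjects assigned to the test group will receive a manual-metering pump containing sufficient" product for the study period, and the control arm takes nothing comparable home.

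**Expectation.** The hypothesis in Background, Aim, & Hypothesis is directional: outcomes "will be more favorable for the FGG donor sites being covered by the test wound dressing material".

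**The concern.** Both secondary comparisons contain a step at which a person decides something: whether a site bubbles, and whether a recording is kept. As the plan stands, the clinician who placed the dressing may take both decisions, knowing the arm and the hypothesis. Subjects and operators cannot easily be masked here. A trace reviewer can be, and a peroxide reader can be in part.

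Two features add to the exposure. A wrong finding of closure is final if testing then stops, so it carries into every later visit, whereas a wrong finding of bubbles can be corrected at the next one. And a rule that removes any recording that might be affected by motion leaves the reviewer wide discretion. At stake is whether a difference between arms in healing or blood flow could be attributed to the dressing.

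**Working it through.** The plan gives no figure on this point. Its power statement concerns pain and is not an input. The calculations below show how much judgement error it would take to matter.

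**Inputs from the plan (Statistical Analysis):** 20 subjects per arm; two-sided Fisher exact test; 4 visits; Bonferroni correction; alpha 0.05. The limit per visit is 0.05 / 4 = 0.0125.

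**Assumptions (not in the plan):** the true closure rate, and the share of readings that are wrong. The overall Williams-adjusted test that precedes the visit-level tests is not modelled.

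**1. How many readings must shift?** Start from 12/20 closed in both arms at one visit, and move readings up in one arm or down in the other.

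| Shifted readings | Resulting table | Two-sided Fisher p |
|---|---|---|
| 4 (all up in one arm) | 16/20 vs 12/20 | 0.30 |
| 6 (smallest p of any split) | 18/20 vs 12/20 | 0.065 |
| 7 (4 up, 3 down) | 16/20 vs 9/20 | 0.048 |
| 7 (smallest p of any split) | 19/20 vs 12/20 | 0.020 |
| 8 (smallest p of any split) | 20/20 vs 12/20 | 0.003 |

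Seven is the minimum for unadjusted p < 0.05, and some splits of seven miss it (14/20 vs 7/20 gives 0.056). Seven never reaches 0.0125; eight does for the most one-sided splits. With Bonferroni, the 16/20 vs 9/20 table gives 4 × 0.0484 = 0.19.

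The counts depend on the starting point. From 0/20 in both arms, p = 2·C(20,k)/C(40,k) for k false closures in one arm. For k = 5 this is 31,008/658,008 = 0.047, and for k = 7 it is 155,040/18,643,560 = 0.008; k = 6 gives 77,520/3,838,380 = 0.020, above 0.0125. Five and seven readings, all in one direction and one arm, are then enough.

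**2. What does consistent misreading do?** Let both arms have true closure rate *p*, and let the reader call a share *e* of still-open test sites closed. The recorded test rate is *p* + (1 − *p*)·*e*. Exact enumeration of all tables at 20 per arm gives the chance of a false difference at one visit:

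| True closure | Limit | e = 0 | e = 20% | e = 30% | e = 40% |
|---|---|---|---|---|---|
| 30% | 0.05 | 2.5% | 9.1% | 17.8% | 30.4% |
| 30% | 0.0125 | 0.4% | 2.9% | 7.7% | 16.9% |
| 50% | 0.05 | 2.0% | 4.9% | 9.2% | 16.3% |
| 70% | 0.05 | 2.5% | 3.7% | 5.4% | 8.2% |

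At 30% closure and *e* = 30%, the recorded rate is 0.30 + 0.70 × 0.30 = 0.51, or on average 0.21 × 20 = 4.2 misread sites, all in one arm. Inflation is greatest while many sites are open and fades as closure approaches.

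**3. LDF.** As an extreme illustration, suppose the highest 10% of values are rejected in one arm only. For a normal distribution the mean moves by −φ(1.2816)/0.9 = −0.1755/0.9 = −0.195 SD. In a simple two-sample t-test with 20 independent values per arm, the noncentrality is 0.195 × √(20/2) = 0.617, and the two-sided rejection rate rises from 5% to about 9%. The sign cannot be read as helping or harming episil, because no section says whether higher or lower flux is favourable.

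**The case against.** Several stronger readings are tempting, and the documents do not support them.

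- *Nobody is masked.* The plan is silent. It supports only that no masking is specified.
- *A few judgement calls decide the result.* Under the plan's own Bonferroni-corrected test they do not. From 12/20 in each arm, four upward misreadings in one arm give p = 0.30. The risk is consistent error in one direction.
- *Any bias will favour episil.* For the peroxide test the hypothesis makes that direction plausible. For LDF it cannot be derived.
- *Both outcomes are subjective readings.* The LDF value is an instrument average, taken through stent holes at a fixed 0.5 mm with a still probe. Judgement enters only through probe handling and rejection.

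Two further objections have force. The LDF model as written contains time, position and patient but no treatment term, so it holds no test between arms to be biased. That is a separate gap; the secondary aim still requires the comparison, and selective rejection would bear on it once made. Also, the plan does not say that recordings are saved or when rejection is decided. If motion is judged at the chairside, coded files mask nothing unless the procedure changes.

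Calling the technique unbiased, and fixing the probe position, is not an answer. Both concern acquisition, not which recordings are discarded. Visible dressing will defeat masking of the peroxide reader at some early visits, but not of a reviewer who sees only traces.

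**Conclusion.** The concern holds in a limited form. The plan specifies no masking for the peroxide reader or for whoever excludes LDF recordings, the arms are visibly different, the hypothesis is directional, and the LDF exclusion rule has no threshold. Systematic misreading or selective rejection could bias the secondary comparisons.

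The size depends on assumed closure and error rates. With 30% true closure, misreading 30% of open test sites raises the false-positive rate at one visit from 2.5% to 17.8% unadjusted, and from 0.4% to 7.7% at the corrected limit. With higher closure or smaller error shares the effect is slight. For LDF, even one-sided rejection of the top 10% gives only about 0.2 SD, in no interpretable direction.

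The change should be made because it is cheap and a peroxide reading cannot be repeated later. The point concerns secondary outcomes only. It does not show that bias will occur, and it does not address self-reported pain.

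**What to change.** 1. **LDF.** Save every recording under a code. State a motion-artifact criterion in advance. Decide exclusion against it with arm and visit hidden, before the allocation list is merged. Report excluded recordings by arm and visit.
2. **Peroxide test.** Name as reader an existing study team member who neither performed nor supervised that subject's surgery and does not know the allocation. Because residents operate under faculty supervision, not having operated is insufficient on its own. Ask subjects not to mention home product use before the reading.
3. **Text.** Reconcile the rule that testing stops at closure with the timeline that lists the test at every visit, since repeat testing would expose a wrong finding of closure. Acknowledge that masking is imperfect while dressing is visible.

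The cost is file coding and a reading rota. No extra subjects, visits or staff are needed, and the sample size is unaffected.

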#### *Surgical Procedures & Postoperative Care*

As stated above, periodontal residents under the direct supervision of periodontal faculty will perform the FGG procedure in all subjects. The FGG procedure will be performed following the surgical technique of Sullivan and Atkins or Miller. The donor tissue for the FGG procedure will be retrieved from either the right or left side of the palate. The FGG donor sites will be of a standardized size of 10 mm x 10 mm. As stated above, subjects in the control group will receive a hemostatic gauze, Surgicel®, covered by a cyanoacrylate dressing, PeriAcryl®90, at the donor site while the subjects in the test group will receive the same brand of hemostatic gauze, Surgicel®, but covered with episil®. Subjects in the test group will be given the remainder of the bottle of episil® with instructions for home application up to 3 times daily. Postoperative instructions will include discontinuing tooth brushing and flossing around the surgical site for the first 3 post-operative weeks. Subjects will be provided with a prescription for ibuprofen (600 mg) to take as needed for analgesia, unless contraindicated. Acetaminophen with 30mg of codeine will be prescribed to subjects unable to ingest ibuprofen.

The LDF measurements in the FGG donor site and on the contralateral side of the palate will be recorded in four sites. A clear acrylic stent will be fabricated for each subject from individual subjects' dental casts. Holes will be made in the stent in four locations on each the right and left sides of the palate. One site located centrally, one close to the mesial, one close to the distal and one close to the apical of the FGG donor site and in the same locations on the contralateral side of the palate will be measured at each of the specified postoperative appointments. The LDF measurement will be performed at baseline prior to surgery, immediately after harvesting of the FGG donor site, and on post-operative days 3, 7, 14 and 21. The LDF measurements will be performed with the tip of the fibre optic probe inserted into the holes of the individual acrylic stent. The LDF probe will be placed at a

standardized location perpendicularly to the tissues and at a distance of 0.5 mm from the tissues and will remain motionless during the LDF measurements.

Below is a summary of the timeline of the study:

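### Laser Doppler blood flow is planned only as change from the pre-surgical reading; a comparison of the dressings would be more precise, by an unknown amount, if it adjusted for that reading

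*Combined protocol and SAP*

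**What the plan says.** Background, Aim, & Hypothesis sets the secondary aim: to "compare gingival healing via measurement of the gingival blood flow at the FGG donor sites". The accompanying hypothesis is that blood flow will be more favourable under the test dressing, so the aim is a comparison of arms.

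Study Population and Design schedules the readings "at baseline prior to surgery, immediately after harvesting of the FGG from donor site, and on post-operative days 3, 7, 14 and 21". Surgical Procedures & Postoperative Care places four probe positions through a fixed stent: "One site located centrally, one close to the mesial, one close to the distal and one close to the apical of the FGG donor site".

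Statistical Analysis then defines the outcome: "Changes of blood flux values in the FGG donor site will be expressed as the difference" between the flux (PU) at a given time and "the individual baseline value of the same site". The model follows: "The observation time and point and the position (mesial, center, distal and apical to the FGG donor site) will be modeled as fixed factors". The change value is the dependent variable, and patient effects are random. The Dunnett tests are there to "evaluate the differences between baseline and subsequent time points and between different positions in the FGG donor site".

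The baseline reading is not a covariate, and no other analysis variable for blood flow is defined. The LDF paragraphs have no dressing term. The between-group Mann-Whitney tests earlier in that section follow the pain-form days (1, 2, 3, 5, 7, 10, 14 and 21), and the text does not tie them to blood flow.

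**The concern.** Using the change score subtracts the whole baseline reading, whatever its relation to the later one. If the baseline predicts later flow only weakly, the subtraction mostly adds the baseline's own variation to the outcome. A covariate lets the data set the weight.

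There is reason to suspect a weak relation here. The baseline is read on intact palate, and every later reading on or beside a wound that is open or healing. With 20 subjects per arm and no power statement for blood flow, avoidable variance matters. At stake is the precision of the between-dressing comparison of a secondary outcome.

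**Working it through.** **The plan's own figures.** None is given for blood flow. The power statement (f = .57, .67 and .83 at n = 40, 30 and 20) refers to the change in pain score. It reproduces as a group-by-time test with noncentrality f²N if six measurements are assumed, a number the plan does not state: power 79.3%, 80.4% and 80.5%. It has no bearing on this point.

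**Inputs.** 20 per arm and two-sided α = 0.05 come from the plan. Assumed, because the documents are silent: ρ, the correlation between baseline and follow-up PU; k, the baseline SD divided by the follow-up SD; and, for power only, a true difference of 0.909 follow-up SDs, which gives 80% power on the follow-up value alone. The calculation is simplified to one reading per patient at one time point.

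**Formulas, in units of the follow-up variance.**
- Follow-up value alone: 1
- Change score: 1 + k² − 2ρk
- Baseline-adjusted: 1 − ρ²
- Change minus adjusted: k² − 2ρk + ρ² = (k − ρ)², which is never negative

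**Equal SDs (k = 1).** The change-score variance becomes 2(1 − ρ), so adjusted/change = (1 − ρ²)/[2(1 − ρ)] = (1 + ρ)/2. Power is from the noncentral t.

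| ρ | Change | Adjusted | Adjusted/change | Power, change | Power, adjusted |
|---|---|---|---|---|---|
| 0 | 2.00 | 1.00 | 0.50 | 50.8% | 79.9% |
| 0.3 | 1.40 | 0.91 | 0.65 | 65.8% | 83.5% |
| 0.5 | 1.00 | 0.75 | 0.75 | 80.0% | 89.8% |
| 0.7 | 0.60 | 0.51 | 0.85 | 95.1% | 97.5% |
| 0.9 | 0.20 | 0.19 | 0.95 | 100% | 100% |

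**Unequal SDs.** Change/adjusted = (1 + k² − 2ρk)/(1 − ρ²):

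| k | ρ = 0 | ρ = 0.3 | ρ = 0.5 | ρ = 0.7 |
|---|---|---|---|---|
| 0.5 | 1.25 | 1.04 | 1.00 | 1.08 |
| 1 | 2.00 | 1.54 | 1.33 | 1.18 |
| 1.5 | 3.25 | 2.58 | 2.33 | 2.25 |

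For example, at ρ = 0.3 and k = 1.5: (1 + 2.25 − 0.90)/0.91 = 2.35/0.91 = 2.58.

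**Small-sample check.** Simulation with 20 per arm and equal SDs (20,000 runs per ρ) gave adjusted/change variance ratios of 0.51, 0.67, 0.77, 0.87 and about 0.98 at ρ = 0, 0.3, 0.5, 0.7 and 0.9. Estimating the slope therefore costs about 2% to 3% of variance (for example 0.67/0.65 = 1.03). Type I error was about 5% for both methods.

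**Within-arm contrasts.** Subtracting a patient's baseline at a site removes the same number from all later readings there. In complete, balanced data, contrasts between post-surgical times are therefore unchanged.

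**The case against.** The strongest reply is that the written LDF analysis contains nothing for the change score to weaken. Its tests compare baseline with later times and positions with each other. For the first, change is the quantity being asked about; contrasts between later times are unaffected. This stands: the missing dressing term is the larger defect, and this point matters only when it is repaired. But the stated aim requires that repair, and adding a dressing term to the model of change scores would leave the precision loss in place.

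A reader might infer more than the documents support, in four ways.
- *That the tissue read at baseline has been removed, so ρ must be low.* This is clear only for the central probe. The other three positions are described as near the edges and may lie on or beside the margin. A low ρ is plausible, not established.
- *That subtraction is worse than ignoring the baseline whenever ρ < 0.5.* The general condition is ρ < k/2, which equals 0.5 only when the SDs are equal.
- *That a definite number of subjects is being wasted.* At ρ = 0.3 and equal SDs, 40 adjusted subjects are worth 40 × 1.54, about 62, analysed by change. With k from 0.5 to 1.5 that becomes about 42 to 103.
- *That the comparison would be biased, or chance baseline imbalance only partly removed.* Randomisation keeps the change score unbiased on average. With equal SDs, subtracting at full weight over-corrects an imbalance, because the right weight is ρ.

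It is also fair to say that one common baseline slope may be too simple for four positions and several healing times, and that a site-level covariate mixes within-patient and between-patient relations.

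**Conclusion.** The point holds as one of efficiency. For the comparison of dressings, an unadjusted change score is valid but, in large samples, never more precise than adjusting for a baseline that is already collected. With equal SDs the adjusted variance is between 0.50 (ρ = 0) and 0.95 (ρ = 0.9) of the change-score variance. With unequal SDs the gain may be nil (k = ρ, where the small cost of estimating the slope remains) or much larger.

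The size for this trial cannot be stated, because the documents give neither the correlation nor any PU SD. The illustrative power figures rest on an assumed effect and one reading per patient. The consequence is confined to precision in a secondary outcome, and depends on the dressing comparison being added. The change is worth making because it needs no new data and has little downside.

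**What to change.** In the LDF paragraphs of Statistical Analysis, state that for comparisons of the two dressings:
- the outcome is the post-surgical PU reading;
- the fixed terms are dressing, time, dressing-by-time and position;
- patient is a random factor;
- the same site's pre-surgical PU is a covariate, with its slope allowed to vary by time if needed. Adding the patient's mean baseline would separate the between-patient relation from the within-patient one.

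Keep the change score for describing the time course within each arm.

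The cost is a short addition to the text and one or a few degrees of freedom. No extra measurements are needed. The sentence should be written together with the missing dressing term, since neither repair achieves the aim efficiently without the other.

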The outcome analysis of the time needed to obtain complete re-epithelialization of the FGG donor site will be made by comparing experimental groups on the frequency distribution of patients experiencing complete re-epithelialization in each of the 4 post-operative visits. The Williams-adjusted log-likelihood ratio was performed, followed by *post-hoc* tests using Bonferroni-corrected Fisher's exact test (2-tailed).

Based on a sample size of  $n = 40$  (20 per group), a repeated measures analysis will have 80% power to detect an effect size of  $f = .57$ . For a sample size of  $n = 30$  (15 per group), the same analysis will have 80% power to detect an effect size of  $f = .67$ , while a sample size of  $n = 20$  (10 per group) will have 80% power to detect an effect size of  $f = .83$ . All of these effect sizes are classified as large effects by Cohen's guidelines (1988), or large differences in the change in pain score between the two groups.

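### Baseline ΔPU is zero by definition, so using baseline as the Dunnett reference in the ΔPU model breaks the equal-variance assumption; leaving it out removes the reference level

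*Combined protocol and SAP*

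**What the plan says.** All of the analysis text is in the LDF paragraphs of the Statistical Analysis section.

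- **Outcome.** ΔPU is the PU value at a site and time, less "and the individual baseline value of the same site".
- **Model.** A univariate general linear model for ΔPU. Observation time and position "will be modeled as fixed factors and the patient as a random factor with the" ΔPU as dependent variable.
- **Condition.** The model is used "after verification of the assumptions of homogeneity of variance and normality of the residual distribution". No test, scale, threshold or fallback is named.
- **Comparison.** A two-sided Dunnett test is used "in order to evaluate the differences between baseline and subsequent time points", and also between positions.
- **Data.** Study Population and Design schedules LDF "at baseline prior to surgery, immediately after harvesting of the FGG from donor site, and on post-operative days 3, 7, 14 and 21", which is six times. Surgical Procedures & Postoperative Care gives four positions: "One site located centrally, one close to the mesial, one close to the distal and one close to the apical of the FGG donor site".

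**The concern.** Dunnett's test compares several levels of a factor with one reference level and uses a pooled error variance. Here the reference is baseline and the response is change from baseline, so the reference group is a column of zeros. The plan also says that equal variance will be verified, and this structure rules it out when baseline is one of the time levels.

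Two things are at stake. If the zeros are entered, the pooled standard error does not match the true uncertainty of a visit's mean change. If they are not entered, the analyst has no reference level for the stated test and must choose a replacement, possibly after seeing the data. The same holds if the homogeneity check fails, because no fallback is given.

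**Working it through.** The plan gives no figure for the LDF analysis to reproduce. Its only power statement is written for the pain score and does not enter here. It also gives no standard deviation for PU or ΔPU, so every variance below is an assumption.

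**1. The baseline level.** For patient i and position j, ΔPU at baseline = PU₀ − PU₀ = 0. With independent reading error of variance σ², ΔPU at any later time has variance σ² + σ² = 2σ². One time level has variance 0 and five have positive variance.

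**2. How many rows.** 40 patients × 4 positions = 160 readings per time, and 160 × 6 = 960 rows. Exact zeros are 160/960 = 1 in 6, before artifact exclusions.

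**3. The homogeneity check.** Levene's test at the 5% level across time levels, on simulated data:

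| Check applied to | Rejected |
|---|---|
| ΔPU, baseline included (10 to 40 patients, all variance settings) | 100% |
| ΔPU, baseline left out | about 1% to 14% |
| Residuals, additive patient term (reading variance 1; patient-by-visit variance 0, 0.25 or 1) | 83% to 100% |
| Residuals, additive patient term, other patient-to-error variance ratios | about 19% to 100% (22% to 100% at 40 patients) |
| Residuals, patient-by-position term | 4% to 27% |

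The last row has an exact reason. ΔPU differs from raw PU by a constant per site, and a site effect absorbs that constant, so the residuals of the two analyses are identical.

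**4. The Dunnett standard error.** Assume independent readings with σ² = 1, no true change, additive time, position and patient terms, and 40 patients.

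- Residual df: 960 − 1 − 5 − 3 − 39 = 912.
- Within-site part: 5 × (160 − 1) = 795 df with expected mean square 1, so the sum of squares is 795.
- Patient-by-position part, which the additive model leaves in the error: 3 × 39 = 117 df. A site's mean ΔPU over six times has variance 1/6 + 1 − 2/6 = 5/6, so the expected mean square is 6 × 5/6 = 5 and the sum of squares is 117 × 5 = 585.
- Expected pooled error: (795 + 585)/912 = 1380/912 = 1.513.
- The true variance of a visit's mean change is 2/160. The test uses 1.513 × 2/160. The ratio of standard errors is √1.513 = 1.23, or 23% too large.

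For 20 patients, (5 × 79 + 5 × 3 × 19)/452 = 680/452 = 1.504, and the ratio is again 1.23.

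**5. Familywise error in that setting.** The large-sample two-sided Dunnett critical value for five comparisons at 5% is about 2.51. Against the true standard error the effective cut-off is 2.51 × 1.23 = 3.09, with a two-sided normal tail of 0.0020. Five comparisons give at most 5 × 0.0020 = 1.0%. Simulations put it between about 0.6% and 2%, against 5% nominal.

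**6. If baseline is not a level.** Time then has five levels, all post-baseline, and Dunnett can compare them only with one of themselves. Change from baseline has to be tested as a mean ΔPU against zero, which the plan does not specify.

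**7. The remedy.** Per-patient mean ΔPU over the four positions, tested against zero at each of the five visits with Holm adjustment, gave familywise error of about 4% to 5% in all simulated settings.

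**The case against.** **The text is looser than a gate.** A reader might infer that the check must fail whatever the data show, so that the only LDF model is never permitted. The documents do not support this. The wording is a routine statement that assumptions will be checked. It names no test and sets no pass/fail rule, and a residual check can pass (step 3). This objection stands. A pass would still not make the variance of ΔPU equal across times.

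**Entry of the zeros is inferred.** The definition of ΔPU sets an observation time point apart from baseline, so observation time could mean the five later times only. That is possible, but the Dunnett sentence then names a reference that is not in the model. Each reading leaves something to repair.

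**The error bars depend on the patient term.** With a patient-by-position effect and independent readings, the pooled error is σ² and the Dunnett standard error is right, zeros included. The plan names only a patient factor, so the additive form is the more direct reading, but it is not certain. The 23% figure holds for that form only.

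**The direction can reverse.** With patient-by-visit variance, familywise error for ΔPU with baseline zeros reached 31% in simulation (range 1% to 31%). That inflation comes from unmodelled correlation within a visit, which is a separate matter, and it is not counted here.

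**The secondary aim is not at stake in this point.** A reader might infer that this defect leaves the comparison of dressings unanswered. The LDF model as written has no dressing term, so it cannot answer that aim whether or not the check passes.

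**Conclusion.** The point holds in a limited form. It is certain from the definition that baseline ΔPU is 0. It follows that, with baseline as a time level, equal variance of ΔPU across times is false by construction and a Levene check on ΔPU by time will fail at this sample size. It is also certain that, without baseline as a level, the stated Dunnett comparison has no reference.

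The effect on inference is conditional. With independent readings and an additive patient term, standard errors are about 23% too large and familywise error is about 1% to 2% at most instead of 5%, so real changes in flow are harder to detect. Other patient terms or correlation within visits change this figure and can change its sign. The outcome is secondary and the comparison is within the donor site, but the correction is nearly free and should be made before the LDF data are analysed.

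**What to change.** - Remove baseline as a level of the time factor. Analyse ΔPU at the five post-baseline times: immediately after harvest and days 3, 7, 14 and 21.
- Test each visit's mean ΔPU against zero, with Holm adjustment over the five visits. This replaces the Dunnett comparison with baseline.
- Either give the model visit-specific variances, or average the four positions to one value per patient and visit. Then no pass/fail homogeneity check is needed.
- Do not offer raw PU with Dunnett as an equivalent. With an additive patient term its familywise error ran from 0.4% to 42% in simulation. It needs patient-by-position and patient-by-visit terms to be valid.

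The cost is a revised paragraph, a few lines of model code and, if the visit-specific model is chosen, a few extra variance parameters. No new data or subjects are needed. The comparison of dressings on blood flow has to be specified separately.
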